Follow-up visit 1 (FU1) = 30 days from the last dose ±7 days or coincide with the date of discontinuation (± 7 days) if date of discontinuation is greater than 37 days after last dose, Follow-up visit 2 (FU2) = 84 days (± 7 days) from follow-up visit 1. Follow up visits 1 and 2 will occur within 100 days of last dose only after subject completes all study treatment. Beyond 100 days from the last dose of study therapy, subjects will be followed for ongoing drug-related AEs until resolved, AE symptoms returned to baseline, or are deemed irreversible, until lost to follow-up, or withdrawal of study consent or death.

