APPENDIX 1 SELECT ADVERSE EVENTS DEFINITION AND CONVENTIONS

The select Adverse Events (select AEs) consist of a list of preferred terms grouped by specific category (e.g. pulmonary events, gastrointestinal events categories) and by subcategory (e.g. thyroid disorders, diabetes, pituitary, adrenal disorders subcategories). These categories and subcategories are defined by the Sponsor and the list that is most current at the time of analysis will be used. Also, changes may be made to this list with each new version of MedDRA.

For information, the select adverse events defined at the time of finalization of the first version of the document are listed in Table A-2 using MedDRA version 20.1. The final list used for the clinical study report will be included in an Appendix of the CSR.

Time-to onset definition

Time-to onset of select AE (any grade) for a specific category (i.e. pulmonary events, gastrointestinal events, ...) is defined as the time between the day of the first dose of study treatment and the onset date of the earliest select AE (of any grade) in this category.

If the subject did not experience a select AE (of any grade) in the category, time-to onset will be censored at the maximum follow-up time of all subjects in their respective treatment group (i.e. for subjects without an event, follow-up time is defined from first dosing date up to last dosing date +30 days (or 100 days depending on the analysis) if subjects are off treatment and followed for at least 30 days (or 100 days depending on the analysis) , otherwise it is defined up to the last known alive date). The resulting Kaplan-Meier plot will represent the cumulative rate of the select AE (any grade) in the category over time.

Time-to onset of select AE (grade 3-5) for a specific category is defined similarly but restricted to grade 3-5 select AEs.

Time-to onset of drug-related (grade 3-5 or any grade) select AE for a specific category is defined similarly but restricted to drug-related select AEs.

Time-to onset for a specific subcategory is defined similarly but restricted to event of this subcategory.

Time-to resolution definition

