In order to derive the time-to resolution, overlapping or contiguous select AEs within a specific category (defined in Table A-2) will be collapsed into what will be termed “clustered” select AEs. For example, if a subject (without pre-treatment AE) experienced an AE from 1st to 5th January, another AE (with different PT but within same category) from 6th to 11th January and same AE from 10th to 12th January, these will be collapsed into one clustered select AE from 1st to 12th January. Table A-1 is summarizing key derivation steps for each type of clustered select AEs.

Time-to resolution of select AE (any grade) for a specific category is defined as the longest time from onset to complete resolution or improvement to the grade at baseline among all clustered select AEs in this category experienced by the subject. Events which worsened into grade 5

events (death) or have a resolution date equal to the date of death are considered unresolved. If a clustered select AE is considered as unresolved, the resolution date will be censored to the last known date alive. Improvement to the grade at baseline implies that all different AE events in the clustered select adverse event should at least have improved to the corresponding (i.e. with same preferred term) baseline grade. This measure is defined only for subjects who experienced at least one select AE in the specific category.

The time-to resolution of select AE (grade 3-5) for a specific category is defined similarly with an onset date corresponding to a grade 3-5 select AE.

Time-to resolution of drug-related select AE (any grade or grade 3-5) is defined similarly but restricted to drug-related select AE.

The time-to resolution of select AE (any grade or grade 3-5, drug-related or all) where immune modulating medication was initiated is defined similarly with the additional condition that the subject started an immune modulating medication during the longest select AE resolution period.

Time-to resolution for a specific subcategory is defined similarly but restricted to event of this subcategory.

Table A-1: Derivation of clustered select AE

Type of clustered select AE	Derivation
Any grade	Collapse any on-treatment select AE from the same category
Drug-related of any grade	Collapse any on-treatment drug-related select AE from the same category

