Grade 3-5	Collapse any on-treatment select AE from the same category. Resolution will be based on the onset date of the earliest grade 3-5 records (if no grade 3-5 record, clustered select AE is excluded)
Drug-related of Grade 3-5	Collapse any on-treatment drug-related select AE from the same category Resolution will be based on the onset date of the earliest grade 3-5 record (if no Grade 3-5 record, clustered select AE is excluded)

The algorithm for collapsing select adverse event records is using the following conventions:

For each subject and specified category, the corresponding adverse event records will be collapsed when:

- 1) Multiple adverse event records have the same onset date.
- 2) The onset date of an event record is either the same day or 1 day later than the resolution date of a preceding event record (contiguous events).
- 3) The onset date of an event record is after the onset date and prior to or on the resolution date of a preceding event record (overlapping events).

Table A-2: Select Adverse Events

Category	Subcategory	Preferred Terms	
ENDOCRINE ADVERSE EVENT	ADRENAL DISORDER	ADRENAL INSUFFICIENCY	
		ADRENAL SUPPRESSION	
		ADRENOCORTICAL INSUFFICIENCY ACUTE	
		BLOOD CORTICOTROPHIN DECREASED	
		BLOOD CORTICOTROPHIN INCREASED	
		HYPOTHALAMIC PITUITARY ADRENAL AXIS SUPPRESSION	
		PRIMARY ADRENAL INSUFFICIENCY	
		SECONDARY ADRENOCORTICAL INSUFFICIENCY	
		DIABETES	DIABETES MELLITUS
			DIABETIC KETOACIDOSIS
	FULMINANT TYPE 1 DIABETES MELLITUS		
	LATENT AUTOIMMUNE DIABETES IN ADULTS		
	TYPE 1 DIABETES MELLITUS		
	PITUITARY DISORDER		HYPOPHYSITIS
		HYPOPITUITARISM	
		LYMPHOCYTIC HYPOPHYSITIS	
		THYROID DISORDER	ATROPHIC THYROIDITIS
	AUTOIMMUNE HYPOTHYROIDISM		
	AUTOIMMUNE THYROIDITIS		
	BASEDOW'S DISEASE		
	BLOOD THYROID STIMULATING HORMONE DECREASED		
	BLOOD THYROID STIMULATING HORMONE INCREASED		
	HYPERTHYROIDISM		
	HYPOTHYROIDISM		
	PRIMARY HYPERTHYROIDISM		
	PRIMARY HYPOTHYROIDISM		
	SILENT THYROIDITIS		
	THYROID FUNCTION TEST ABNORMAL		
	THYROID HORMONES DECREASED		
	THYROID HORMONES INCREASED		
	THYROIDITIS		
	THYROIDITIS ACUTE		
THYROXINE DECREASED			
THYROXINE FREE DECREASED			
THYROXINE FREE INCREASED			
THYROXINE INCREASED			
TRI-IODOTHYRONINE UPTAKE INCREASED			
GASTROINTESTINAL ADVERSE EVENT		AUTOIMMUNE COLITIS COLITIS	

Table A-2: Select Adverse Events

Category	Subcategory	Preferred Terms

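### Table A-1 collapses only on-treatment records, so a select AE that continues in a record starting after the window can get too short a time to resolution, or be left unresolved

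*SAP*

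**What the plan says.** **What a cluster is.** SAP Appendix 1, under the time-to-resolution definition, says that "overlapping or contiguous select AEs within a specific category (defined in Table A-2) will be collapsed" into one clustered event. No on-treatment condition is attached. The three conventions after Table A-1 also work on dates alone: records join if they share an onset date, if the later onset is "either the same day or 1 day later than the resolution date of a preceding event record", or if "The onset date of an event record is after the onset date and prior to or on the resolution date of a preceding event record".

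**What Table A-1 collapses.** The any-grade row says "Collapse any on-treatment select AE from the same category". The Grade 3-5 row says "Collapse any on-treatment select AE from the same category. Resolution will be based on the onset date of the earliest grade 3-5 records". The two drug-related rows carry the same on-treatment restriction and add drug-relatedness.

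**How the subject's value is formed.** It is the longest cluster in the category. A cluster resolves only when every event in it has resolved or returned to its baseline grade. An unresolved cluster is censored at the last known date alive.

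**The window.** Appendix 1 mentions 30 or 100 days once, when setting follow-up for subjects without an event in the time-to-onset analysis: "last dosing date +30 days (or 100 days depending on the analysis". The SAP does not define on-treatment for AEs. Section 7.1 uses 100 days for extended follow-up AE summaries, and Section 7.4.3 defines on-treatment as up to 100 days for concomitant medications. Section 7.6.2.2 refers time to resolution to the CA209 Core Safety SAP version 5, which is not among the documents.

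**The endpoint and the data.** Median time to resolution of select AEs is a secondary endpoint (Protocol Section 8.3.2, SAP Section 4.2.1). The footnote to Protocol Table 5.1-5 says: "Beyond 100 days from the last dose of study therapy, subjects will be followed for ongoing drug-related AEs until resolved".

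**The concern.** The purpose of clustering is that one episode of, say, gastrointestinal toxicity is measured once, from start to end, however many lines it occupies on the case report form. A filter applied to each record before collapsing defeats this for episodes that straddle the end of the window. The same illness then gets a different duration depending on whether it was entered as one record or two.

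The situation is plausible here. Protocol Section 4.5.6 calls for permanent discontinuation of nivolumab after Grade 3 drug-related diarrhoea, colitis or pneumonitis of any duration, so much of the course of such events falls after last dose, where the filter acts.

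At stake are the secondary time-to-resolution results, mainly those for Grade 3-5 events. The subset analysis of events treated with immune-modulating medication is also exposed. It requires the medication to have started during the subject's longest resolution period, so a shortened period could remove a subject from that subset. Incidence, and therefore the primary endpoint, does not depend on how long a cluster lasts.

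**Working it through.** **1. The SAP's own example.** Records of 1-5, 6-11 and 10-12 January are sorted by onset and merged when an onset is no later than the preceding resolution date plus 1 day. The result is one cluster, 1-12 January, as the SAP states.

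Now suppose that the on-treatment window ended during that example, and keep only records whose onset lies inside it:

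| Last on-treatment day (assumed) | Records kept | Cluster ends |
|---|---|---|
| 10 January | all three | 12 January |
| 8 January | 1-5, 6-11 | 11 January |
| 5 January | 1-5 | 5 January |

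The middle row shows that the end is the resolution date of the last record kept, not the end of the window.

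**2. Two rules compared on assumed records.** Days are counted from last dose, and length = end − start + 1. Rule A is Table A-1 read literally (keep records starting in the window, then collapse). Rule B collapses all records and keeps clusters that start in the window.

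| Window | Records | Rule A | Rule B |
|---|---|---|---|
| 30 days | 20-45, 46-90 | 45 − 20 + 1 = 26 | 90 − 20 + 1 = 71 |
| 30 days | 20-30, 31-90 | 30 − 20 + 1 = 11 | 71 |
| 30 days | 20-90 (one record) | 71 | 71 |
| 100 days | 20-45, 46-90 | 71 | 71 |
| 100 days | 90-110, 111-150 | 110 − 90 + 1 = 21 | 150 − 90 + 1 = 61 |

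**3. The longest-cluster rule.** Take a 30-day window and records from Day −60 to 10, 25-32 and 33-60. Rule A gives clusters of 71 and 8 days; Rule B gives 71 and 36. The longest is 71 under both, so the subject's value does not change. It changes only if the omitted record ends later than those kept and the affected cluster is, or would become, the longest.

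**4. Direction.** If the last record kept closes at resolution or at the baseline grade, Rule A scores the cluster as resolved, too early. If it closes at a grade change still above baseline, the baseline-grade condition is not met. The cluster is then unresolved and censored at the last known date alive, which works the other way.

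**5. Illustration of size.** The documents give no inputs, so all of these are assumed: onset uniform over the stated days after last dose; Grade 3, 2 and 1 stages entered as three contiguous records with exponential lengths; a shortened cluster scored as resolved where it stops; 400,000 clusters per scenario.

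| Window | Onset, days after last dose | Mean stage, days | Clusters losing a record | Median, B to A (days) |
|---|---|---|---|---|
| 30 days | 0-21 | 14 | 60% | 37 to 27 |
| 30 days | 0-21 | 21 | 76% | 56 to 33 |
| 100 days | 0-21 | 14 | 1% | 37, unchanged |
| 100 days | 0-21 | 21 | 8% | 56, unchanged |
| 100 days | 0-100 | 14 | 28% | 37 to 32 |

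The window and the timing of onset drive the result. The set-up favours a large effect: every onset is after last dose, every grade step is a new record, and the longest-cluster rule is not applied.

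**The case against.** The strongest reply is that this is an ambiguity, not an established error. Table A-1 is presented as a summary of key steps. The meaning of on-treatment for AEs, and whether filtering precedes collapsing, may be settled in the Core Safety SAP. That stands as a limit on certainty. But Table A-1 is this study's written derivation, and as written it is narrower than the text and conventions around it.

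One could also say that a second preferred term first arising after the window is a late new event, and that one window for incidence and resolution is a legitimate choice. It is, if stated. The SAP's own example, however, collapses a different preferred term of the same category into one episode.

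Four stronger readings are tempting and are not supported:

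- **Events are cut at the window edge.** No rule does this. A record that starts in the window keeps its full length.
- **A 30-day window governs time to resolution.** The 30 days appear only in the censoring of time to onset; the two other windows that the SAP states are 100 days.
- **The necessary data are all collected and then discarded.** After Day 100, ongoing drug-related AEs are followed and related SAEs are reported (Protocol Section 6.1.1), but non-serious AEs need be collected only for a minimum of 100 days (Section 6.2.1). Late continuation records will be uneven.
- **The simulated percentages estimate the bias.** They illustrate a mechanism under assumed inputs. No passage says that each grade change is a new record; the reference to the earliest Grade 3-5 record fits that practice but also fits a cluster of several preferred terms.

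**Conclusion.** The point holds as an internal inconsistency in Appendix 1 that can mis-measure a named secondary endpoint. It rests on reading on-treatment as a condition on each record's onset, which is the natural reading of Table A-1. Under it, time to resolution can be too short, or a cluster can be left unresolved, for subjects whose longest episode continues in a record that starts after the window.

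The size cannot be derived from the documents. It is potentially material if a 30-day window applies. With a 100-day window it is small for events starting soon after last dose, and larger only for events starting late in the window. Single-record events and the primary endpoint are unaffected. A reader should not conclude that reported times to resolution would be wrong in general, or that any bias must run towards faster resolution. The change is worth making because the rule is explicit, the endpoint is named and the remedy is short.

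**What to change.** In SAP Appendix 1:

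1. State the on-treatment window, in days after last dose, that is used for clustering.
2. Apply it only to the record that opens the cluster; in the two Grade 3-5 rows, to the first Grade 3-5 record.
3. Then collapse all later overlapping or contiguous records of the same category, whether or not they start on-treatment. In the drug-related rows, collapse drug-related records only.
4. Leave the incidence window unchanged.

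Suggested wording for the Grade 3-5 row: *If the first Grade 3-5 record is on-treatment, collapse all overlapping or contiguous select AE records of the same category, including later records that start after the on-treatment window.* The other three rows change in the same way.

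The cost is a sentence or two and a small programming change; no new data are needed. Some times to resolution become longer. After Day 100 new non-serious records are not systematically collected, so continuation there rests on follow-up of ongoing drug-related AEs and on related SAEs. A table footnote should say so.
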